Prior work demonstrated that the glutamine to glutamate ratio (Gln/Glu) is a sensitive measure of cortical glutamate-glutamine cycle dysfunction in severe psychiatric disorders. In our prior MRS study, 6 weeks of 10 Hz rTMS modulated cortical glutamatergic tone in depressed adolescents. Baseline, posttreatment, and 6 month follow up MRS 3 T scans examined glutamate concentrations in 8 cm voxels from the left dorsolateral prefrontal and anterior cingulate cortices (Figure1). Spectroscopic data were collected with an optimized, intermediate echo time, point resolved spectroscopy (PRESS) sequence and 2-dimensional J-resolved averaged PRESS sequence. After 6 weeks of rTMS, mean Gln/Glu ratios increased from baseline and at 6 month follow-up in both voxels with both sequences. Mixed model repeated measures analysis revealed a significant negative relationship between depression severity as assessed with the CDRS-R and the Gln/Glu ratio in the dorsolateral prefrontal cortex ($\hat{b} = -0.00127$; 95% CI, -0.00207 to -0.00048 ; raw $P=.003$; false discovery rate $P=.01$). Hence, throughout treatment and follow-up period, decreases in depressive symptom severity had an indirect relationship to increases in the Gln/Glu ratio. This initial work presents many unanswered questions. Resolving GABA, glutamate, and glutamine at 3 T in a single acquisition is challenging to impossible. Special techniques can be used to quantify each of the neurochemicals separately, but that results in three different acquisitions which dramatically increases acquisition time. Our current methodologies do not adequately resolve cortical GABA concentrations and may yield imprecise measures of glutamine concentrations as Cramer-Rao lower bounds (CRLB) criteria are suboptimal. Current work with 7 T MRS demonstrates promise in resolving and quantifying GABA, glutamate, and glutamine in a single acquisition. To our knowledge, 7 T MRS has not been used to study adolescent depression previously.^{63,64}

Ultra-High Field MRS for Biomarker Development in Adolescent Depression

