1.6 Anticipated Duration of the Clinical Investigation

It is anticipated that the proposed study will be five years in duration. For individual participants, Phase I (biomarker stratified, randomized trial of 1 Hz vs. 10 Hz rTMS) is 10 weeks in duration. Phase II (trial of cTBS vs iTBS based on ICF biomarker status) is 3 weeks in duration.

2 Study Objectives

The proposed study is a dose finding, effectiveness, and target validation study of rTMS for adolescent depression with a biomarker stratified design.⁷² Intracortical facilitation (ICF),⁶⁵ a transcranial magnetic stimulation (TMS) measure of cortical glutamatergic tone is the target engagement biomarker for the proposed trial. In phase I, a cohort of adolescents (ages 12-18) with clinically significant depression defined as 40 or greater on the Children's Depression Rating Scale-Revised (CDRS-R) will be stratified according to baseline ICF (high defined as > 1.5 or low defined ≤ 1.5) and then randomized to 6 weeks of either left prefrontal 1 Hz or 10 Hz rTMS. The research team will collect weekly ICF and CDRS-R measures during treatment. We will assess baseline anhedonia with a composite measure from relevant CDRS-R and Beck Depression Inventory-II (BDI-II) items. We will assess lifetime adversity with the Childhood Trauma Questionnaire (CTQ).

Participants in Phase I will be offered the opportunity to have 3 and 7 T MRI and MRS looking for biomarkers at baseline and after 6 weeks of treatment. A subgroup of depressed adolescent participants (up to 50) who do not respond to 1 Hz or 10 Hz rTMS will be offered the opportunity to participate in an exploratory, 2 week, trial of iTBS or cTBS based on ICF biomarker status (Phase II of the study). Participants with high baseline ICF (defined as > 1.5) will be assigned to cTBS treatment. Participants with low ICF (defined ≤ 1.5) will be assigned to iTBS.

7 T MRS measures Glutamate and GABA biomarkers in healthy adolescents and depressed adolescents. The overall goals are to examine cortical Glutamate and GABA neurochemical markers in adolescent depression and the impact of 1 Hz and 10 Hz rTMS on cortical glutamate and GABA neurochemical markers when compared to the healthy adolescent cohort.

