2.2 Secondary Objective

Aim 2 examines changes in weekly ICF and CDRS-R across 6 weeks of either 1 Hz or 10 Hz rTMS.

- We anticipate that ICF measures will decrease in depressed adolescents receiving 6 weeks of 1 Hz rTMS.
- We anticipate that ICF measures will increase in depressed adolescents receiving 6 weeks of 10 Hz rTMS.

Depressive symptom improvement will have a direct relationship with ICF decrease in depressed adolescents receiving 6 weeks of 1 Hz rTMS and an indirect relationship with ICF increase in depressed adolescents receiving 10 Hz rTMS.

Exploratory Aim 3

Aim 3a: To compare 7 T MRS cortical measures of GABAergic tone and glutamatergic neurochemistry in depressed adolescents and healthy control adolescents.

Aim3b: To examine potential changes in cortical GABAergic and glutamatergic neurochemistry after a six week course of either 1 Hz or 10 Hz rTMS in depressed adolescents.

Hypothesis:

1. Depressed adolescents will have decreased cortical levels of GABA as assessed with 7 T MRS compared to healthy control adolescents.
2. Depressed adolescents will have increased cortical levels of Glutamate as assessed with 7 T MRS compared to healthy control adolescents.
3. Bilateral cortical 7 T MRS measures of GABA will increase after 6 weeks of 1 Hz rTMS in depressed adolescents.
4. Bilateral cortical 7 T MRS measures of Gln/Glu will decrease after 6 weeks of 1 Hz rTMS in depressed adolescents.
5. Bilateral cortical 7 T MRS measures of GABA will decrease after 6 weeks of 10 Hz rTMS in depressed adolescents.

6. Bilateral cortical 7 T MRS measures of Gln/Glu will increase after 6 weeks of 10 Hz rTMS in depressed adolescents.

Exploratory Aim 4 examines clinical moderators of treatment (anhedonia and adversity) in this sample of adolescents undergoing treatment with 1 Hz and 10 Hz rTMS.

Hypothesis:

6 weeks of low frequency (1 Hz) rTMS vs. high frequency (10 Hz) rTMS will have greater efficacy (as assessed by CDRS-R) in depressed adolescents with anhedonia and adversity compared to depressed adolescents without anhedonia and adversity

The proposed project will examine an rTMS dosing, target engagement strategy for adolescent depression and refine understanding of GABAergic and glutamatergic contributions to negative valence. Findings will inform the clinical dissemination of rTMS for adolescent depression and provide insights to further treatment innovation for disorders of the negative valence systems domain early in life.^{9,52}

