MIXED procedures (mixed model approach) in SAS software will make use of all available data from all participants from the efficacy analysis set, and provide a robust mechanism for handling data that are assumed missing at random (see sensitivity analysis section below for MNAR).

Secondary Aim

Data Analysis Plan for Secondary Aim 2 (Hypotheses 2a–2d)

Secondary Continuous Outcome: Intracortical Facilitation (ICF)

Intracortical Facilitation over the 6-week study period will be the secondary continuous outcome measure. A within-Participants linear mixed model analysis of repeated measures will be used to examine the change in ICF over 6 weeks of rTMS treatment in depressed adolescents. We will consider the inclusion of pubertal state and treatment resistance (as defined by ATHF score) during the study period as a covariate in the mixed model. A mixed model analysis will be conducted on ICF for those who receive 6 weeks of low frequency (1 Hz) rTMS treatment (Hypothesis 2a) and, in a separate model, for those who receive 6 weeks of high frequency (10 Hz) rTMS treatment (Hypothesis 2c). Restricted maximum likelihood estimation, Type 3 tests of fixed effects, and generalized least squares (LS) will be used, with the Kenward-Roger correction applied to the appropriate and best fitting covariance structure. The sandwich (robust covariance matrix) estimator will also be considered. LS mean contrasts (between ICF measurement time periods) from the mixed model will also be examined. A separate linear mixed model analysis similar to that described above will also be implemented over 6 weeks of acute rTMS treatment and throughout the 6-month follow-up period. A nonlinear mixed model will be considered (e.g., exponential decay/growth model) to estimate ICF over the 6 weeks of rTMS treatment (if the pattern of ICF values suggests that a nonlinear model is deemed necessary).

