A linear mixed model repeated measures analysis similar to that described above will also be used to examine the relationship between measures of ICF (as the response variable) and depressive symptoms (CDRS-R total as a time-varying covariate) over the 6 weeks of rTMS treatment. We will consider the inclusion of pubertal state and treatment resistance (as defined by ATHF) during the study period as a covariate in the mixed model. The parameter estimates (regression coefficients) will be interpreted from the solution for fixed effects in the mixed model analysis for those who receive 6 weeks of low frequency (1 Hz) rTMS treatment (Hypothesis 2b) and for those who receive 6 weeks of high frequency (10 Hz) rTMS treatment (Hypothesis 2d). A separate linear mixed model analysis similar to that described above will also be implemented over 6 weeks of acute rTMS treatment and throughout the 6-month follow-up period. A nonlinear mixed model will be considered to estimate ICF over the 6 weeks of rTMS treatment from CDRS-R total (if the pattern of ICF and CDRS-R total suggests that a nonlinear model is deemed necessary).

Data Analysis Plan for Exploratory Aim 3 (MRI/MRS)

A within-participants linear mixed model analysis of repeated measures will be used to examine baseline differences between depressed adolescents and healthy control adolescents (Hypotheses 1 and 2); and the change in cortical MRS measures of GABA and Gln/Glu over 6 weeks of rTMS treatment in depressed adolescents. Separate mixed models will be conducted on cortical GABA and Gln/Glu for those who receive 6 weeks of low frequency (1 Hz) rTMS treatment

(Hypotheses 3 and 4) and for those who receive 6 weeks of high frequency (10 Hz) rTMS treatment (Hypotheses 5 and 6). A nonlinear mixed model will be considered (if the pattern of GABA and Gln/Glu values suggests that a nonlinear model is deemed necessary).

Data Analysis Plan for Exploratory Aim4

Moderator Effects of Anhedonia and Adversity on Treatment Outcome of Depression Severity

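### Hypotheses 2b and 2d concern change within a participant, but the single planned CDRS-R coefficient blends within-person and between-person association

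*Combined protocol and SAP*

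**What the plan says.** Section 2.2 (repeated in 1.5.1) gives the hypotheses that Section 7.2 labels 2b and 2d. For 1 Hz: "Depressive symptom improvement will have a direct relationship with ICF decrease in depressed adolescents receiving 6 weeks of 1 Hz rTMS". For 10 Hz: "an indirect relationship with ICF increase in depressed adolescents receiving 10 Hz rTMS".

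Section 7.2 tests them with a mixed model used to "examine the relationship between measures of ICF (as the response variable) and depressive symptoms (CDRS-R total as a time-varying covariate"). It adds: "The parameter estimates (regression coefficients) will be interpreted from the solution for fixed effects in the mixed model analysis", separately for each rTMS arm.

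The model's fixed effects are not listed. It is said only to resemble the one described before it, which for 2a and 2c reads: "A within-Participants linear mixed model analysis of repeated measures will be used to examine the change in ICF". The only further covariates under consideration are pubertal state and ATHF score. No participant-mean term, deviation term or change-score version appears anywhere in 7.2.

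Two other places bear on how the result will be read. Section 2 says that ICF "is the target engagement biomarker for the proposed trial". Section 1.1 interprets a mixed-model coefficient relating Gln/Glu to CDRS-R in an earlier study as follows: "decreases in depressive symptom severity had an indirect relationship to increases in the Gln/Glu ratio".

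**The concern.** The hypotheses pair improvement with ICF change in the same participant. They do not ask whether more depressed adolescents have a higher or lower ICF than less depressed ones. A single CDRS-R covariate that varies both between and within participants answers both questions with one number.

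Two errors can follow. A stable correlation between a participant's usual CDRS-R and usual ICF can make the coefficient significant when ICF does not follow symptoms at all. A stable correlation of the opposite sign can hide a real link. Section 1.1 already reads a coefficient of this kind as change going with change, so the same reading is likely here. 2b and 2d are the only planned tests that link ICF change to symptom change.

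**Working it through.** **Inputs from the documents.** 25 participants per cell, so 2 × 25 = 50 per rTMS arm (7.1). Within-participant CDRS-R correlation at most 0.50 with compound symmetry (7.1), taken as a CDRS-R ICC of 0.5. Baseline plus six weekly paired measurements, so m = 7 (5.3, Table 3). Two-sided alpha 0.05.

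**Assumptions.** The ICF ICC (0.3 to 0.7) and the correlation r between participants' stable CDRS-R and ICF levels are not in the documents. The model is a random intercept with visit as a categorical effect, complete data, and no truncation of CDRS-R by the entry criterion.

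**1. The plan's own figure.** The documents give no power figure for 2b and 2d. The primary-aim figure reproduces. The variance factor is (1 + 5 × 0.5)/6 = 0.583, and n = 2 × (1.960 + 0.842)² × 0.583/0.61² = 24.6, so 25 per group. The inputs are being read as the plan meant them.

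**2. Weight of the between-person part.** In a random-intercept model the slope is a precision-weighted mean of the within-person and between-person slopes, with relative weights

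- W = (m − 1)(1 − ICC_CDRS)/(1 − ICC_ICF)
- B = (1 + (m − 1)ICC_CDRS)/(1 + (m − 1)ICC_ICF)

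With both ICCs at 0.5, W = 6 and B = 1, so the between-person share is 1/7 = 14.3%. The extremes over ICCs of 0.3 to 0.7 are:

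- CDRS-R 0.3, ICF 0.7: W = 14, B = 2.8/5.2 = 0.538, share 3.7%
- CDRS-R 0.7, ICF 0.3: W = 2.571, B = 5.2/2.8 = 1.857, share 41.9%

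**3. False positives when the true within-person slope is zero.** Simulated arms of 50 participants and 7 visits, REML, both ICCs 0.5, 2,000 to 4,000 arms per setting. A range is shown where repeated runs differ.

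| r | single CDRS-R covariate | deviation term |
|---|---|---|
| 0 | 5% | about 5% |
| 0.1 | 6% | about 5% |
| 0.2 | 7–9% | about 5% |
| 0.3 | 11–13% | about 5% |
| 0.5 | 22–24% | about 5% |
| 0.7 | 43–45% | about 5% |

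The size agrees with step 2. At r = 0.5 the slope of participant means is 0.25/(0.5 + 0.5/7) = 0.4375, and 0.4375/7 = 0.063. The simulated mean coefficient is 0.066.

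**4. Sensitivity to the ICCs at r = 0.5.**

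- CDRS-R at 0.5: 34% with ICF ICC 0.3, and 14% with ICF ICC 0.7.
- ICF at 0.5: 14% with CDRS-R ICC 0.3, and 43% with CDRS-R ICC 0.7.
- Both moved together (4,000 arms each): about 9% with CDRS-R 0.3 and ICF 0.7, and about 54% with the reverse.

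The settings with a CDRS-R ICC of 0.7 lie above the plan's own bound of 0.50.

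**5. If baseline CDRS-R is carried over from the Aim 1 model.** The rate falls to about 7% at r = 0.3 and 11% at r = 0.5. It is still above nominal.

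**6. Masking.** With a true within-person slope of 0.15 and r = −0.5, power is 28–31% for the single covariate and 72–74% for the deviation term. At r = −0.3 it is 43% against 73%.

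**7. Which sign does the trial expect?** Section 2.1 predicts that high-ICF participants improve more on 1 Hz and low-ICF participants more on 10 Hz. On treatment, that makes the between-person slope of ICF on CDRS-R negative on 1 Hz and positive on 10 Hz. Hypotheses 2b and 2d predict within-person slopes that are positive on 1 Hz and negative on 10 Hz. If Aim 1 is right, the two parts pull against each other in both arms.

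**The case against.** Several points on the other side stand.

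- A reader might infer that the trial's test of target engagement is compromised. It is not. Whether rTMS moves ICF is tested by 2a and 2c, whose description includes no CDRS-R covariate.
- A reader might infer that a trait correlation could produce the whole predicted result. One present before randomization has the same sign in both arms in expectation, while the plan predicts opposite signs. In two-arm simulations with zero within-person slope, both hypotheses were supported in at most 0.1% of trials. But 7.2 interprets each arm separately, so one hypothesis can still be falsely supported.
- The highest rates need r = 0.7, or a CDRS-R ICC above the plan's bound. At r of 0.2 or less the inflation is small, and at r = 0 there is none.
- The plan does not say that CDRS-R is uncentred, and its wording is loose enough to admit a baseline covariate. Such a covariate reduces the blending without removing it. A different covariance structure changes the weights, and the Kenward-Roger correction and sandwich estimator act on the standard errors. None of these separates the two components.

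What does not stand is treating this as missing detail only. The model as stated has one CDRS-R coefficient, and that coefficient is the quantity to be interpreted.

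**Conclusion.** The concern holds for 2b and 2d. The stated coefficient estimates a blend, while the hypotheses are about the within-person part. That much follows from the algebra.

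The size of the harm is less certain, because it rests on an assumed r and ICF ICC. With both ICCs at 0.5 the slope is mostly within-person. Even so, the per-arm error rate roughly doubles at r = 0.3 and is more than four times nominal at r = 0.5. Loss of power is a realistic risk because the trial's own Aim 1 predictions imply between-person slopes opposite to those of 2b and 2d.

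The matter is confined to half of one secondary aim, and it should be corrected before analysis.

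**What to change.** In Section 7.2, for 2b and 2d:

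- Replace the single CDRS-R covariate with two terms: each participant's mean CDRS-R over the analysed visits, and the weekly deviation from that mean.
- State that visit (time) is a fixed effect. Otherwise trends over time shared by ICF and CDRS-R also enter the slope.
- Base 2b and 2d on the deviation term only. Report the participant-mean term as descriptive.
- State the predicted sign of the deviation coefficient: positive on 1 Hz, negative on 10 Hz. This matches Section 1.1, where a negative coefficient is called an indirect relationship.

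The cost is one derived variable, one extra parameter per model and a sentence or two of text. The test gives up the between-person information, which does not bear on these hypotheses.

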| 
Statistical Methodology
 | 
For the primary aim, a linear mixed model analysis of repeated measures will be used to evaluate the repetitive transcranial magnetic stimulation (rTMS) by biomarker status interaction effect on depression severity (CDRS-R score) over 6 weeks of rTMS.
 
For the secondary aim, a within-participant linear mixed model analysis of repeated measures will be used to examine the change in ICF over 6 weeks of rTMS.
 
For the exploratory aims, a within-subjects linear mixed model analysis of repeated measures will be used to examine the change in cortical MRS measures of GABA, glutamate, and glutamine over 6 weeks of rTMS treatment in depressed adolescents. A multiple mediation/moderation path analytic model will be used to estimate the direct effect as well as the total and specific indirect effects of rTMS treatment on depression severity (at the 6-week endpoint) through each potential baseline moderator (anhedonia and adversity).
 |

1 Introduction

This document is a protocol for a human research study. This study will be carried out in accordance with the procedures described in this protocol, applicable United States government regulations and Mayo Clinic policies and procedures.

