Hence for the present protocol we have designed an effectiveness and target validation trial of 1 Hz vs. 10 Hz rTMS. While the inclusion of a sham arm would be ideal, there are substantial pragmatic and financial barriers to completing such a study as a single site while concurrently addressing other critical National Institute of Mental Health (NIMH) priorities. Studies of 1 Hz rTMS and mechanistic studies of rTMS in adolescents would address a substantial knowledge gap and could provide further innovations. Unfortunately, there is a low probability that this will be studied systematically outside of a federally funded grant and even less likely that the neurobiologic mechanisms associated with 1 Hz and 10 Hz rTMS in adolescent depression will be adequately studied.

Developmentally informed, targeted interventions with rTMS for adolescent depression could reap important gains on an individual and population level as cortical, GABAergic and glutamatergic tone continues to change throughout development setting the stage for important future functions.^{17,53} Prior rTMS research focused on depression often has a fatal flaw as heterogeneous groups of patients have been studied with insufficient clinical characterization.^{33,52} Anhedonia⁵⁴ and adversity^{55,56} in depressed adolescents are important dimensional traits to quantify in terms of GABAergic tone, glutamatergic tone, and treatment responsivity to 1 Hz and 10 Hz rTMS. Examining a cohort of depressed adolescents and healthy controls with TMS neurophysiology would deepen our understanding of the role of GABA and glutamate in the negative valence systems domain.^{56,57}

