3.1 General Design

Phase I will enroll a cohort (N=120) of adolescents (ages 12-18) with clinically significant depression defined as 40 or greater on the Children’s Depression Rating Scale-Revised (CDRS-R). Participants will be stratified according to baseline ICF (high defined as > 1.5 or low defined ≤ 1.5) and then randomized to 6 weeks of either left prefrontal 1 Hz or 10 Hz rTMS. The research team will collect weekly ICF and CDRS-R measures during treatment. We will assess baseline anhedonia with a composite measure from relevant CDRS-R and Beck Depression Inventory-II (BDI-II) items. We will assess lifetime adversity with the Childhood Trauma Questionnaire (CTQ). Participants will have baseline neurocognitive testing. Participants will have a six month follow-up visit with depression severity measures (CDRS-R and BDI-II) and neurocognitive assessments.

Up to 100 Depressed adolescents will be offered the opportunity to undergo magnetic resonance spectroscopy (MRS) measure at baseline (prior to any Phase I TMS treatment) and posttreatment visits (within 2 months after 6 weeks of TMS treatment in Phase I). A comparison group of 30 healthy control adolescents will be offered the opportunity to undergo MRS at one time point. A subset of up to 50 depressed adolescents who do not respond to Phase I TMS treatment will be offered the opportunity to continue in Phase II (within 2 months of completion of Phase I treatment) for two weeks of either iTBS if (ICF ≤ 1.5) or cTBS if (ICF is >1.5).

Magnetic Resonance Imaging: Depressed and control participants will undergo 3 T structural MRI and ultra-high field (7 T) MRS (7-T, 90-cm horizontal bore magnet interfaced with a Siemens console) to examine GABA, glutamate, and glutamine concentrations in the occipital cortex (OCC). [name] is a co-investigator on this grant and will supervise the collection and analyses of all MRI/MRS data at the Center for Magnetic Resonance Research (CMRR) at the University of Minnesota. Please note that travel time from Mayo Clinic Rochester to the CMRR is approximately 1 hour. Participants will be remunerated for travel and all study visits.

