4.1.1 Inclusion Criteria Healthy Controls

- ages 12-18, male or female

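### Aim 3a: the depressed-versus-control MRS comparison is labelled within-participants, states no between-group term, and names no age, sex or puberty covariate although the groups are unmatched

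*Combined protocol and SAP*

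**What the plan says.** The only analysis text for Aim 3a is one clause in section 7.2, under the plan for Exploratory Aim 3: "A within-participants linear mixed model analysis of repeated measures will be used to examine baseline differences between depressed adolescents and healthy control adolescents". The clause ties this comparison to Hypotheses 1 and 2. Hypothesis 1 is lower cortical GABA in depression. Hypothesis 2, in section 2.2, reads: "Depressed adolescents will have increased cortical levels of Glutamate as assessed with 7 T MRS compared to healthy control adolescents". After a semicolon the same sentence turns to a second analysis, "the change in cortical MRS measures of GABA and Gln/Glu over 6 weeks of rTMS treatment in depressed adolescents", which serves Hypotheses 3 to 6.

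On the data, section 3.1 says: "A comparison group of 30 healthy control adolescents will be offered the opportunity to undergo MRS at one time point". Up to 100 depressed adolescents are offered a scan at baseline and another after treatment, and spectra come from one occipital voxel.

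The whole inclusion list for controls (section 4.1.1) is "ages 12-18, male or female". Section 4.2.2 adds exclusions for psychiatric history or treatment, pregnancy, a positive drug screen and MRI contraindications. No matching is described.

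On covariates, section 7.2 will consider pubertal state in the Aim 1 and Aim 2 models and controls for it in Aim 4. The Aim 3 paragraph names no covariate. Section 1.1 states that "GABAergic and glutamatergic tone continues to change throughout development".

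**The concern.** A patient-control difference at baseline, with one value per person, contains no within-participant information. Calling the model within-participants and leaving the group term unstated means that the effect of interest is not written into the model.

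The covariate gap matters more. Randomisation protects the comparison of 1 Hz with 10 Hz, but nothing protects the comparison of patients with controls. Two groups that both span ages 12 to 18 can still differ in mean age, sex mix or pubertal stage. If the metabolite varies with those characteristics, the unadjusted difference mixes development with depression, and could create a difference or hide one. As written, the plan provides for puberty adjustment in Aims 1, 2 and 4 but not in the one comparison that has no randomisation behind it. It is also the only use of the control data that section 7.2 describes.

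**Working it through.** The plan gives no effect size, SD or power for Aim 3, so there is no figure of its own to reproduce. Its only power statement concerns the primary aim.

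**Inputs from the documents**
- Depressed participants scanned: up to 100 (section 3.1).
- Controls scanned: 30, at one time point (section 3.1).
- Test level: two-sided 0.05 (section 7.2).

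**Inputs assumed, because the documents give none**
- Imbalance in age or puberty between the groups: 0.25 to 0.5 SD.
- Correlation of age or puberty with the metabolite: 0.2 to 0.5.

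**Step 1. Standard error of the unadjusted difference, in SD units**

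SE = √(1/100 + 1/30) = √0.0433 = 0.208.

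**Step 2. Spurious difference**

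Spurious difference = imbalance × correlation.
- Low end: 0.25 × 0.2 = 0.05 SD.
- Middle case: 0.5 × 0.3 = 0.15 SD.
- High end: 0.5 × 0.5 = 0.25 SD.

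**Step 3. False-positive rate when depression has no effect**

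With k = spurious difference / SE, the rate is approximately Φ(−1.96 + k) + Φ(−1.96 − k). The last column uses the noncentral t distribution with 128 degrees of freedom.

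| Spurious difference | k | Normal formula | Noncentral t |
|---|---|---|---|
| 0.05 SD | 0.24 | 5.7% | 5.7% |
| 0.15 SD | 0.72 | 11.1% | 11.0% |
| 0.25 SD | 1.20 | 22.5% | 22.2% |

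**Step 4. Fewer than 100 depressed participants**

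The spurious difference does not depend on sample size. With 50 against 30, SE = √(1/50 + 1/30) = 0.231, and the noncentral t rates at 0.05 and 0.25 SD are 5.5% and 18.8%. The conclusion does not rest on reaching 100.

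**Step 5. Can a mixed model give the contrast?**

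One data set was simulated with 100 depressed participants scanned twice and 30 controls scanned once. A mixed model with group and time terms gave a baseline group difference of −0.186 (SE 0.186). Ordinary regression on the baseline scans gave −0.186 (SE 0.183). So a mixed model is workable here. What the plan lacks is the stated group term.

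**The case against.** **The label.** One sentence covers two analyses, and within-participants is apt for the second. The sentence also states its target, a difference between depressed and control adolescents. A reader might infer that the model cannot deliver that contrast. The documents do not support this: depressed participants have two scans, and a mixed model with a group term estimates the baseline difference (step 5). The label is loose and the term is missing, but the analysis is not impossible. Section 3.1 also mentions test-retest studies in controls, without a schedule. A repeat control scan would still leave depressed-versus-control a between-participant contrast.

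**Glutamate.** Because the paragraph writes out only GABA and Gln/Glu, a reader might infer that glutamate is left out and Hypothesis 2 has no test. That is not so. The baseline comparison is assigned to Hypotheses 1 and 2 by number, and Hypothesis 2 is glutamate. The GABA and Gln/Glu wording belongs to the change analysis, whose hypotheses concern exactly those measures.

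**The size.** Both groups share one age range, and an imbalance biases the result only if the variable also correlates with the metabolite in the occipital voxel. The documents give no such correlation. An imbalance of 0.5 SD is 0.5/0.208 = 2.4 standard errors, about a 1.6% event if both groups came from one distribution; 0.25 SD is 1.2 standard errors, about 23%. This stands as a caution about the top of the range. It is only a benchmark, since controls are recruited separately and are not a random draw from the same population as patients.

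**Importance.** Aim 3 is exploratory. That stands, and it limits the weight of the point.

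**Conclusion.** The point holds in a limited form. The Aim 3a model is mislabelled and under-specified, and its comparison of unmatched groups has no stated adjustment for age, sex or puberty. With 100 against 30, the assumed ranges give a spurious difference of 0.05 to 0.25 SD and false-positive rates from about 6%, close to nominal, to about 22%. These figures show what could happen; they do not predict what will. The False Discovery Rate adjustment in section 7.2 addresses multiple testing and would not remove this bias.

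The primary endpoint (CDRS-R) and the secondary endpoint (ICF) are untouched. This is a free improvement to an exploratory aim.

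**What to change.** In section 7.2, separate the two analyses that now share a sentence.

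- **Hypotheses 1 and 2:** specify a between-group linear model on the single baseline scan, or a mixed model with an explicit group term. Name GABA and glutamate as the outcomes, so that the reader need not trace the hypothesis numbers. Prespecify age, sex and pubertal stage as covariates.
- **Hypotheses 3 to 6:** keep the within-participant models as they are.

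The cost is SAP wording only. The Pubertal Development Scale is scheduled at baseline for depressed participants (Tables 2 and 3). The notes to Table 3 list a pubertal scale and a demographics form for controls. Age and sex are known for everyone enrolled. No new data, visits or participants are needed. The three covariates use a few of the 128 residual degrees of freedom available at 100 against 30, or of the 78 available at 50 against 30.
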